14 SAFETY ANALYSES

The safety summaries will be presented based on the Safety Analysis Set. Safety variables include AEs, clinical laboratory variables, vital signs, physical examinations, ECG and GCAS variables. Safety variables will be summarized by double-blind treatment group and overall using descriptive statistics. For each continuous measure in clinical laboratory variables, vital signs, and electrocardiogram, change from Baseline results will be presented in two ways as specified in [Section 5.1](#).

14.1 Adverse Events

All AEs will be coded using the MedDRA Version 19.0 or newer.

An AE (classified by preferred term) will be considered a TEAE if it started on and after the first open-label study dose date and no later than the last open-label study dose date + 30 days. If any AE started before the completion of procedures at the Week 12 visit in Study ACP-103-032, it will be considered as TEAE in Study ACP-103-032 but not in Study ACP-103-033.

The event counts and the number and percentage of subjects reporting TEAEs will be tabulated by SOC and preferred term; and, by SOC, preferred term, and maximum severity. If more than 1 AE occurs with the same preferred term for the same subject, then the subject will be counted only once for that preferred term using the most severe occurrence for the summarization by severity. In addition, the event counts and the number and percentage of subjects with TEAEs classified by the Investigators as related to the study drug, with most frequently reported TEAEs (preferred terms reported by $\geq 5\%$ of subjects in the Safety Analysis Set, with treatment-emergent serious AEs (TESAEs), with fatal AEs (i.e. events that cause death), and with TEAEs leading to discontinuation of study drug will be summarized by SOC and preferred term. These tables will be sorted alphabetically by SOC and then by descending subject frequency for the preferred terms in the Safety Analysis Set within each SOC.

The event counts and the number and percentage of subjects with any TEAEs will also be tabulated by preferred term without SOCs. This table will be sorted by descending subject frequency in the Safety Analysis Set.

An AE listing by subject will display all events, including those which are not treatment-emergent, and will include the verbatim term in addition to the MedDRA SOC and preferred term. This listing will also include all relevant eCRF data associated with the event: e.g. date of onset, date resolved, date of open-label first dose, date of open-label last dose, severity, frequency, outcome, relationship to study drug, action taken with study drug, and required therapy. When a date is presented, the study day associated with the date will also be displayed. Separate listings will be presented for subjects with SAEs, subjects with AEs leading to discontinuation and subjects who died (if any). In these listings, an indicator for treatment-emergent events and the dose at onset will also be included.

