7 ADVERSE EVENTS/SERIOUS ADVERSE EVENTS AND REPORTING

7.1 Adverse Events

Adverse events occurring after the completion of procedures at the Week 12 visit in the double-blind Study ACP-103-032 will be recorded in the open-label Study ACP-103-033. Adverse events during ACP-103-033 will be recorded through the follow-up safety assessment (conducted by telephone call) approximately 30 days after the last dose of open-label study drug. All ongoing AEs from Study ACP-103-032 will be carried over and will be recorded from Baseline until resolution, or through the Week 52 (EOS/ET) visit. All

AEs must be either resolved or stable at the Week 52 (EOS/ET) visit. For those that are ongoing at the end of the study, the subject should be referred for appropriate treatment.

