The causality of each AE should be assessed and classified by the Investigator as “related” or “not related.” An event is considered related if there is “a reasonable possibility” that the event may have been caused by the product under investigation (i.e., there are facts, evidence, or arguments to suggest possible causation).

Consider the following when assessing causality:

- Temporal associations between the agent and the event,
- Response to cessation (de-challenge) or re-challenge,
- Compatibility with known class effect,
- Known effects of concomitant medications,
- Pre-existing risk factors,
- A plausible mechanism, and
- Concurrent illnesses.

Duration

The duration of the AE should be recorded using the following criteria:

- **Start:** Date of the first episode of the AE or date of significant sustained worsening in severity
- **Stop:** Date when AE either ceased permanently or changed in severity

Frequency

The frequency of the AE should be indicated according to the following definitions:

- **Single:** Experienced once, without recurrence
- **Recurrent:** More than one discrete episode with the same severity

Action Taken with Investigational Drug

- **Dose not changed:** No change in study drug
- **Dose reduced:** Dose of study drug reduced
- **Dose increased:** Dose of study drug increased
- **Drug interrupted:** Investigational drug temporarily stopped
- **Drug withdrawn:** Investigational drug discontinued permanently

Therapy

- **None:** No new treatment instituted
- **Medication:** New treatment initiated as a direct result of AE
- **Other:** Other action required

Outcome

- **Recovered/resolved:** Recovered or resolved
- **Recovered/resolved with sequelae:** Recovered or resolved with sequelae
- **Not recovered/not resolved:** Not recovered or not resolved
- **Fatal:** Death related to AE
- **Unknown:** Unknown

Seriousness

- Not serious
- Serious: Refer to definition in [Section 7.3](#)

In the event that a subject is withdrawn from the study because of an AE, the subject should be followed and treated by the Investigator until the AE has resolved, stabilized, or a new chronic baseline has been established.

The Investigator must record all observed AEs and all reported AEs. At each visit, the Investigator should ask the subject a nonspecific question (e.g., “Have you noticed anything different since your last visit?”) to assess whether any AEs have been experienced since the last report or visit.

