2.1.2 Safety Endpoints

- Serious AEs (SAEs) and withdrawals due to AEs
- Global Clinician Assessment of Suicidality (GCAS)
- Clinically important changes from Baseline in vital sign measurements, weight, clinical laboratory assessments, physical examinations, and electrocardiograms (ECGs)

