- ^e Any untoward medical occurrence that occurs after the completion of procedures at the Week 12 visit in double-blind Study ACP 103-032 should be recorded as an AE, even if dosing for ACP-103-033 has not begun.
- ^f Study drug will be dispensed to the subject at either scheduled or unscheduled visits.
- ^g Study drug will be dispensed to the subject to take home at the Baseline visit. The subject and their study partner/caregiver will be provided instructions to take the first dose of study drug on the following day.
- ^h To be completed at unscheduled visits where there is a dose change.

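### SAP 14.1 limits the SAE and discontinuation tables to treatment-emergent events, a limit that the safety endpoint and Protocol 9.7.2 do not contain and SAP 19 does not declare

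*SAP*

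**What the plan says.** **Treatment-emergent rule (SAP 14.1).** The lower bound is "An AE (classified by preferred term) will be considered a TEAE if it started on and after the first open-label study dose date" and the upper bound is "no later than the last open-label study dose date + 30 days". For an AE that began before the parent study's Week 12 procedures were complete, "it will be considered as TEAE in Study ACP-103-032 but not in Study ACP-103-033". The section makes no exception for such an AE if it later becomes serious or ends treatment.

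**Tables and listings (SAP 14.1).** The serious-event and discontinuation tables are restricted to treatment-emergent events. The fatal-event table is not worded that way. All SAEs, AEs leading to discontinuation and deaths are listed with a treatment-emergent indicator.

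**Collection (Protocol 7.1 and 7.2, SAP Table 1 footnote e).** "Adverse events occurring after the completion of procedures at the Week 12 visit in the double-blind Study ACP-103-032 will be recorded" in ACP-103-033, and an event after those procedures "should be recorded as an AE, even if dosing for ACP-103-033 has not begun". For events already under way, "All ongoing AEs from Study ACP-103-032 will be carried over and will be recorded from Baseline until resolution", or through the Week 52 visit. An AE's start is the "Date of the first episode of the AE or date of significant sustained worsening in severity".

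**Endpoint.** SAP 2.1.2 gives the first safety endpoint as "Serious AEs (SAEs) and withdrawals due to AEs". Protocol 9.7.2 promises summaries of serious AEs, fatal AEs and AEs leading to discontinuation. Neither place restricts them to treatment-emergent events. SAP 19 records no changes to the protocol's analyses.

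**The concern.** The study tests no hypotheses, so its descriptive safety tables are its result. SAEs and withdrawals due to AEs are the events for which single cases matter most in a 52-week extension of about 111 subjects.

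The SAP narrows both tables through a date rule and does not declare the narrowing. The protocol carries unresolved parent-study AEs into the extension and follows them there. An event can therefore become serious, or end treatment, while the subject is taking open-label drug and still be left out of the table meant to count it. The discontinuation table could also show fewer AE withdrawals than the disposition table, with nothing in the SAP to explain the difference.

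**Working it through.** The documents state no event count or rate on this point, so there is no figure to reproduce. The check sets the rules side by side and applies them to test cases.

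**Step 1: endpoint against table.** The endpoint (SAP 2.1.2) and Protocol 9.7.2 both cover SAEs and AE withdrawals with no onset limit. The SAP 14.1 tables cover only those with onset from first open-label dose to last dose + 30 days. The difference is every SAE or AE withdrawal recorded in ACP-103-033 whose recorded start precedes the first open-label dose.

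**Step 2: what moves the start date.** Protocol 7.2 gives a new start date at significant, sustained worsening in severity, and a change in severity closes the old record. Seriousness is a separate classification made in addition to severity (Protocol 7.3). Withdrawal of study drug is recorded under action taken (Protocol 7.2). Neither resets the start date.

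**Step 3: rule applied to cases.**
- Parent-study AE that becomes serious on open-label drug with no severity change: the start stays in ACP-103-032, so it is not a 033 TEAE and not in the SAE table.
- Parent-study AE that causes open-label withdrawal with no severity change: same start, so it is not in the discontinuation table.
- Parent-study AE that worsens in severity on, say, open-label day 40 and is re-recorded: the new start falls inside the window, so it is a 033 TEAE and is counted.
- Non-fatal SAE after the Week 12 procedures but before the first open-label dose date, in a subject later dosed: it is recorded in 033 but starts before the window, so it is not in the SAE table.
- Fatal AE with a start before first dose: it appears in the fatal-event table as worded, but not in the SAE table, although a fatal event is serious by Protocol 7.3.

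**Step 4: size per event.** Planned enrolment is up to about 111 (SAP 3.5). One omitted subject changes an incidence by 1/111 = 0.9 percentage points; three change it by 3/111 = 2.7.

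**Step 5: length of the pre-dose gap.** The first dose is due the day after the Baseline visit (Protocol 3.4.3), and the rule works by date, so on schedule only the rest of the visit day is uncovered. AE rates are not given. I assume 1 to 5 AEs of any kind per person-year.
- Half a day (assumed): 111 × 0.5/365.25 = 0.152 person-years, or 0.15 to 0.76 AEs.
- One full day (upper bound on schedule): 111 × 1/365.25 = 0.304 person-years, or 0.3 to 1.5 AEs.
- First dose seven days late (assumed): 111 × 7/365.25 = 2.127 person-years, or 2.1 to 10.6 AEs.

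These are AEs of every kind; SAEs would be a fraction of them. The gap matters little unless dosing is delayed. The number of carried-over AEs that turn serious or end treatment cannot be derived from the documents.

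**The case against.** The strongest reply is that the rule is ordinary practice. A treatment-emergent count normally starts at first dose. Assigning each AE to one study also avoids counting it in both parent and extension. Worsening in severity is largely covered by the new start date in Protocol 7.2, and many events that become serious will also be rated more severe. Nothing disappears: SAEs and AEs leading to discontinuation have dedicated listings, the disposition table (SAP 6) counts withdrawals by reason, and the fatal-event table is not limited.

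Much of this stands. It justifies the TEAE window itself. It does not justify applying that window to two tables whose endpoint has no such limit, or declaring no change from the protocol. A listing gives no incidence, and the disposition table names no event term.

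A reader might infer more than the documents support:
- *That pre-dose gap events belong to neither study.* SAP 14.1 does not say where the parent study's own window closes, and the ACP-103-032 SAP is not available.
- *That most gap events follow double-blind pimavanserin.* The documents give no roll-over numbers by parent-study arm.
- *That every parent-study AE that escalates is lost, or appears only in a listing.* Severity worsening, the fatal-event table and disposition contradict this.
- *That a specific number of subjects will be missing.* Any such figure needs carry-over and escalation rates that the documents do not contain.

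**Conclusion.** The point holds in limited form. SAP 14.1 narrows the SAE and discontinuation tables relative to the endpoint and Protocol 9.7.2, and SAP 19 does not say so. The events affected are carried-over AEs that turn serious or cause withdrawal without a severity-based new start date, and non-fatal SAEs before first open-label dose in subjects later dosed. A pre-dose AE that later ends treatment falls under the same rule. Subjects never dosed lie outside the Safety Analysis Set and are not part of this point.

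The undercount follows from a stated rule, but its size is unknown: 0.9 percentage points per omitted subject if about 111 enrol. The conclusion assumes that sites apply the Protocol 7.2 start-date rule as written. SAP 14.1 does not say how split records of one AE are handled.

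**What to change.** Change SAP 14.1 as follows.

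1. Keep the first-dose window for the general TEAE tables.
2. For the Safety Analysis Set, tabulate all SAEs and all AEs leading to discontinuation recorded in ACP-103-033, whatever their onset. Give separate rows for onset in ACP-103-032, onset between the Week 12 procedures and first open-label dose, and onset on open-label treatment. The treatment-emergent subset remains visible.
3. Add an exception to the sentence that assigns earlier AEs to the parent study: an AE ongoing from ACP-103-032 that becomes serious or leads to discontinuation on or after the first open-label dose is also a 033 TEAE. State that an AE already re-recorded under Protocol 7.2 for worsening severity is counted once only.
4. Footnote the tables to say that some AEs appear in both studies' tables, so the two must not be added together.

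If the sponsor prefers to keep treatment-emergent tables only, SAP 19 should record that as a departure from Protocol 9.7.2 and give the reason.

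The cost is a few sentences and an onset flag in programming. No new data are needed, because start dates, seriousness and action taken are already collected. The downside is slightly higher event counts and some overlap with the parent study, which the footnote covers.

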14.2 Clinical Laboratory Variables

Clinical laboratory tests are performed at Baseline, Weeks 4, 12, 28 and 52/ET visits.

- Chemistry serum tests include the following

- Sodium (Na), potassium (K), chloride (Cl), phosphorus (P), calcium (Ca), carbon dioxide (CO₂), blood urea nitrogen (BUN), creatinine (CR), uric acid
- Alanine aminotransferase (ALT/SGPT), aspartate aminotransferase (AST/SGOT), gamma-glutamyl transpeptidase (GGT), alkaline phosphatase (ALP), total bilirubin (TBIL), lactate dehydrogenase (LDH)
- HbA1c, glucose
- Albumin (ALB), total protein
- Prolactin
- Creatine kinase (CK)/creatinine phosphokinase (CPK)
- Lipid panel
 - Total cholesterol, HDL-cholesterol, triglycerides, LDL-cholesterol, cholesterol/HDL ratio, Non-HDL cholesterol
- Serum pregnancy test for women of childbearing potential
- Hematology tests include the following:
 - Complete blood count (CBC) including:
 - White blood cell (WBC) count
 - Complete differential (relative and absolute)
 - Hematocrit (Hct), hemoglobin, red blood cells (RBC), platelets
 - Reticulocytes
- Urinalysis tests include the following:
 - Blood, RBCs, WBCs, protein, glucose, ketones, specific gravity, pH
 - Urine pregnancy test for women of childbearing potential.

All laboratory test results are from a central laboratory and will be listed. The listings will include date and study day of collection. All units will be displayed in Système International [SI] units. Out of range values will be flagged in the data listings (e.g., ‘L’ or ‘H’).

Clinical laboratory values reported as continuous values for hematology, chemistry and urinalysis will be summarized using descriptive statistics at Baseline and each scheduled post-Baseline visits. The change from Baseline values will also be summarized at each scheduled post-Baseline visits. The overall minimum and maximum post-Baseline observed

and change from Baseline values will also be summarized. For hemoglobin, hematocrit and uric acid, the above summaries will be presented for each gender as well as for both genders combined. For urinalysis with categorical results, the number and percentage of subjects will be tabulated by category at Baseline and each scheduled post-Baseline visits. For the categorical urinalysis by-visit summary, the denominator is the total number of subjects with non-missing values for the given parameter, visit and double-blind treatment group.

The laboratory values will also be summarized in shift tables to determine the number and percentage of subjects with values classified as below (low), within (normal) and above (high) normal ranges at each scheduled post-Baseline visits relative to the same classification at the Baseline visit. The shifts from Baseline to overall post-Baseline minimum and overall post-Baseline maximum will also be presented. For the by-visit shift summary, the denominator is the number of subjects with non-missing values at Baseline and the given visit for the given parameter and double-blind treatment group. For the summaries of shift to the overall post-Baseline minimum or maximum, the denominator is the number of subjects with non-missing Baseline and at least 1 post-Baseline value for the given parameter and double-blind treatment group. For hemoglobin, hematocrit and uric acid, the shift summaries will be presented for each gender as well as for both genders combined.

Number and percentage of subjects with potentially clinically important (PCI) laboratory values at each scheduled post-Baseline visits and overall post-Baseline will be summarized by Baseline status (all and within normal range) for selected parameters. PCI criteria are listed in [Table 5](#) and [Table 6](#). For the overall post-Baseline summaries, all post-Baseline values will be considered, including unscheduled and out of window values. Subjects with multiple PCI values for a given parameter will be counted only once for that parameter. For the by-visit summary, the numerator for the percentage is the number of subjects with a post-Baseline PCI laboratory value for the given parameter, visit and double-blind treatment group, and the denominator is the number of subjects with non-missing values for the given parameter, visit and double-blind treatment group. For the overall post-Baseline summary, the numerator for the percentage is the number of subjects with at least 1 post-Baseline PCI laboratory value for the given parameter and double-blind treatment group and the denominator is the number of subjects with at least 1 post-Baseline laboratory value for the given parameter and double-blind treatment group. For hemoglobin, hematocrit and uric acid, the count and percentage of subjects with PCI values will be presented for each gender as well as for both genders combined. A listing of all PCI values in study ACP-103-033 will be provided. This listing will include all observations from study ACP-103-033 for those subjects and parameters for which at least 1 PCI value (including Baseline) was observed.

Table 5 Criteria for Potentially Clinically Important Laboratory Values – Hematology and Chemistry

Analyte	Conventional Unit	Low PCI Criteria	High PCI Criteria	SI Unit	Low PCI Criteria	High PCI Criteria
Hematology (whole blood)						
Hemoglobin (male)	g/dL	<11	>18	g/L	<110	>180
Hemoglobin (female)	g/dL	<10	>17	g/L	<100	>170
Hematocrit (male)	%	<30	>55	L/L	<0.3	>0.55
Hematocrit (female)	%	<30	>50	L/L	<0.3	>0.5
Leukocyte (White Blood Cell Count)	x 10 ³ /uL	≤2.8	≥15	x 10 ⁹ /L	≤2.8	≥15
Neutrophils	x 10 ³ /uL	≤1.5	No upper limit	x 10 ⁹ /L	≤1.5	No upper limit
Platelet Count	x 10 ³ /uL	≤75	≥700	10 ⁹ /L	≤75	≥700
Chemistry (serum or plasma)						
ALT (SGPT)	U/L	No lower limit	≥3 X ULN	U/L	No lower limit	≥3 X ULN
AST (SGOT)	U/L	No lower limit	≥3 X ULN	U/L	No lower limit	≥3 X ULN
Total Bilirubin	mg/dL	No lower limit	≥1.5 ULN	umol/L	No lower limit	≥1.5 ULN
BUN	mg/dL	No lower limit	≥30.0	mmol/L	No lower limit	≥10.71
Creatine Kinase (CK)	U/L	No lower limit	≥3 ULN	U/L	No lower limit	≥3 ULN
Sodium	mEq/L	≤125	≥155	mmol/L	≤125	≥155
Potassium	mEq/L	≤3.0	≥5.5	mmol/L	≤3.0	≥5.5
Calcium, total	mg/dL	<8.0	>11.0	mmol/L	<2.0	>2.75
Lactate Dehydrogenase (LDH)	U/L	No lower limit	≥3 X ULN	U/L	No lower limit	≥3 X ULN
Alkaline Phosphatase	U/L	No lower limit	≥3 X ULN	U/L	No lower limit	≥3 X ULN
Uric acid (male)	mg/dL	No lower limit	≥10.5	umol/L	No lower limit	≥624.75
Uric acid (female)	mg/dL	No lower limit	≥8.5	umol/L	No lower limit	≥505.75
Albumin	g/dL	≤2.6	≥6.0	g/L	≤26	≥60
Total Protein	g/dL	≤5.0	≥10.0	g/L	≤50	≥100
Chloride	mEq/L	≤85	≥120	mmol/L	≤85	≥120
Glucose (random)	mg/dL	≤45.1	≥200.0	mmol/L	≤2.48	≥11
Serum Creatinine	mg/dL	Not Applicable	>1.5 ULN	umol/L	Not Applicable	>1.5 ULN
Triglycerides	mg/dL	Not Applicable	>300	mmol/L	Not Applicable	>3.39
Gamma-Glutamyl Transferase (GGT)	U/L	Not Applicable	≥3 ULN	U/L	Not Applicable	≥3 ULN

Table 6 Criteria for Potentially Clinically Important Laboratory Values – Urinalysis

Urinalysis (qualitative dipstick)	Low PCI Criteria	High PCI Criteria
Blood (Occult Blood)	Not Applicable	$\geq+2$
Protein	Not Applicable	$\geq+2$
Glucose	Not Applicable	$\geq+2$

The pregnancy results (positive or negative) for female subjects will be presented in a listing.

14.3 Vital Signs

Vital signs are assessed at Baseline, Weeks 2, 4, 8, 12, 20, 28, 36, 44, and 52/ET visits.

Vital signs including weight, height (measured at ACP-103-032 Screening visit), and the derived BMI will be summarized using descriptive statistics at Baseline and all scheduled post-Baseline visits. The change from Baseline values will also be summarized at the scheduled post-Baseline visits.

Vital sign values will be considered PCI if they meet both the observed value criteria and the change from Baseline criteria listed in [Table 7](#). The number and percentage of subjects with post-Baseline values that are PCI will be summarized at each scheduled post-Baseline visit and for overall post-Baseline. For the overall post-Baseline summaries, all post-Baseline values will be considered, including unscheduled and out of window values. Subjects with multiple PCI values for a given parameter will be counted only once for that parameter. For the by-visit summary, the numerator for the percentage is the number of subjects with a post-Baseline PCI vital sign for the given parameter, visit and double-blind treatment group and the denominator is the number of subjects with non-missing values for the given parameter, visit and double-blind treatment group. For the overall post-Baseline summary, the numerator for the percentage is the number of subjects with at least 1 post-Baseline PCI vital sign for a given parameter and double-blind treatment group and the denominator is the number of subjects at least 1 post-Baseline vital sign for the given parameter and double-blind treatment group. A listing of all PCI values in study ACP-103-033 will be provided. This listing will include all observations from study ACP-103-033 for those subjects and parameters for which at least 1 PCI value (including Baseline) was observed.

Table 7 Criteria for Potentially Clinically Important Vital Signs

Vital Sign Parameter	Unit	Criteria ^a		
		Observed Value	And/Or	Change Relative to Baseline
Systolic blood pressure	mmHg	≥180	And	Increase of ≥20
		≤90	And	Decrease of ≥20
Diastolic blood pressure	mmHg	≥105	And	Increase of ≥15
		≤50	And	Decrease of ≥15
Pulse	bpm	≥120	And	Increase of ≥15
		≤50	And	Decrease of ≥15
Weight	kg	Not Applicable		Increase of ≥7%
				Decrease of ≥7%

^a A post-Baseline value is considered as a PCI value if it meets both criteria for observed value and change from Baseline.

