9.7.3 Clinical Laboratory Values

Descriptive statistics for clinical laboratory parameters, including changes from baseline, will be tabulated by treatment group and timepoint.

The number and percentage of subjects with potentially clinically important post-baseline laboratory values will be summarized by treatment group and timepoint, as well as across all post-baseline timepoints, for selected parameters. The potentially clinically important criteria will be specified in the SAP.

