9.7.4 Vital Signs and Body Weight

Descriptive statistics for vital signs and body weight, including changes from baseline, will be tabulated by treatment group and timepoint. The number and percentage of subjects with changes from baseline (increases and decreases separately) in body weight of 7% or more will also be provided.

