14.4 Electrocardiogram (ECG)

Electrocardiograms are performed at Baseline, Weeks 4, 12, 28 and 52/ET visits. All tracings will be evaluated by a central reading laboratory. ECG data summaries will be performed using the centrally evaluated data.

Observed values of ECG variables (heart rate, PR interval, RR interval, QRS interval, QT interval, and QTc intervals) and the changes from Baseline at each assessment timepoint will be summarized at Baseline and each scheduled post-Baseline visit.

QTc intervals include QTcB (Bazett’s formula) and QTcF (Fridericia’s formula). QTcF will also be categorized into the following categories (msec) and the number and percentage of subjects in each category will be summarized at each scheduled visit and overall post-Baseline maximum:

- Observed: ≤450, 451 to 480, 481 to 500, and >500
- Change from Baseline: ≤10, 11 to 30, 31 to 60, and >60

Electrocardiogram values will be considered PCI if they meet the criteria listed in [Table 8](#). The number and percentage of subjects with post-Baseline PCI values will be summarized at each scheduled post-Baseline visit and for overall post-Baseline. For the overall post-Baseline summaries, all post-Baseline values will be considered, including unscheduled and out of window values. Subjects with multiple PCI values for a given parameter will be counted only once for that parameter. For the by-visit summary, the numerator for the percentage is the number of subjects with a post-Baseline PCI ECG for the given parameter, visit and double-blind treatment group and the denominator is the number of subjects with non-missing values for the given parameter, visit and double-blind treatment group. For the

overall post-Baseline summary, the numerator for the percentage is the number of subjects with at least 1 post-Baseline PCI ECG for the given parameter and double-blind treatment group and the denominator is the number of subjects with at least 1 post-Baseline ECG value for the given parameter and double-blind treatment group. A listing of all PCI values in study ACP-103-033 will be provided. This listing will include all observations from study ACP-103-033 for those subjects and parameters for which at least 1 PCI value (including Baseline) was observed

Table 8 Criteria for Potentially Clinically Important ECG Values

ECG Parameter	Unit	High PCI Criteria
QRS Interval	msec	≥120
PR Interval	msec	≥220
QTcB or QTcF	msec	>500
QTcB or QTcF: change from Baseline	>60 msec	

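### SAP 14.3 does not say that weight gains and losses of 7% or more are counted separately, as Protocol 9.7.4 requires; read literally, it pools them

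*SAP*

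**What the plan says.** Protocol 9.7.4 (Vital Signs and Body Weight) plans descriptive statistics and, for weight, the number and percentage of subjects with "changes from baseline (increases and decreases separately) in body weight of 7% or more".

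SAP 14.3 (Vital Signs) handles weight within the PCI summary:

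- Across all post-Baseline values, the section states that "the numerator for the percentage is the number of subjects with at least 1 post-Baseline PCI vital sign for a given parameter"; this is taken within each original treatment arm. The by-visit numerator is also defined per parameter, visit and group. Neither mentions direction.
- The counting rule is: "Subjects with multiple PCI values for a given parameter will be counted only once for that parameter".
- Table 7 has a single parameter, Weight, with no observed-value criterion and two change criteria on separate lines: an increase of at least 7%, and "Decrease of ≥7"%.

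SAP 19 reports no changes to the analyses specified in the protocol. SAP 1 says that the specifications for tables, figures and listings are kept in a separate document.

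**The concern.** The protocol sets a reporting rule for weight, and the SAP's counting rule, applied as worded, does not deliver it. The SAP defines its counts by parameter. Weight is one parameter, so a subject who gains 7% and a subject who loses 7% both count as a PCI subject for Weight.

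The two directions have different safety meanings, and a pooled figure cannot be separated again from the table. Clinically important weight change is one of the listed safety endpoints (Protocol 2.1.3, SAP 2.1.2) in a study whose primary objective is safety and tolerability. Protocol 1.2 also reports decreased weight as one of the most frequent adverse events (12.4%) in the long-term open-label studies in Parkinson's disease psychosis. That is an adverse-event rate in another disease, not a rate on the 7% criterion, and the protocol itself cautions that these uncontrolled rates are hard to interpret. It does show why a reader would want loss on its own.

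**Working it through.** The plan gives no figure to reproduce. The check compares the texts and then uses a simple count to show what a pooled row would hide.

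**Step 1: what each text asks for.**

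| Item | Protocol 9.7.4 | SAP 14.3 and Table 7 |
|---|---|---|
| Threshold | 7% or more | 7% or more |
| Unit of counting | Subject, by direction | Subject, by parameter |
| Increases and decreases | Separate | Two criteria under one parameter; no statement on separate counts |
| Subject meeting both over time | In both counts | Once for the parameter |

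The thresholds agree. The unit of counting does not.

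**Step 2: what the literal rule produces.** Let L be subjects with at least one loss of 7% or more, G those with at least one gain of 7% or more, and B those with both at different times. Protocol 9.7.4 asks for L and G. The overall numerator in SAP 14.3 is L + G − B.

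At a single visit the once-only rule adds nothing, because SAP 5.3.2 selects one assessment per window. The pooling there comes from the per-parameter numerator alone.

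**Step 3: whether L and G appear elsewhere.**

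- The descriptive summaries of weight change give means, medians and extremes. Gains and losses can offset each other in the mean, and no count above a threshold results.
- The PCI listing shows every observation for a flagged subject, so direction can be found subject by subject. It gives no count or percentage by group.
- Weight loss reported as an adverse event is tabulated under its preferred term, but that depends on investigator reporting and not on the 7% criterion.
- Shift tables to the post-Baseline minimum and maximum exist for laboratory values (SAP 14.2), not for weight.

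None of these supplies what 9.7.4 requires.

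**Step 4: illustration (assumed counts).** Take N = 111, the approximate maximum enrolment in SAP 3.5, with every subject contributing a post-Baseline weight. Borrow 12.4% as an assumed loss rate: 0.124 × 111 = 13.8, so L = 14 and 14/111 = 12.6%. Vary the assumed gain rate from 0% to 12.4%, with B = 0.

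| Assumed gain rate | G | Pooled count | Pooled % | Loss on its own |
|---|---|---|---|---|
| 0% | 0 | 14 | 12.6% | 12.6% |
| 5% | 6 | 20 | 18.0% | 12.6% |
| 10% | 11 | 25 | 22.5% | 12.6% |
| 12.4% | 14 | 28 | 25.2% | 12.6% |

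With equal L and G and complete overlap (B = 14), the pooled figure falls back to 14/111. In the other direction, a reported 28/111 fits any loss count from 0 to 28.

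**The case against.** The strongest reply is that pooling is nowhere stated as an intention. The once-only rule follows directly after the sentence admitting all post-Baseline values, including unscheduled and out-of-window ones, so its natural purpose is to stop repeat values from being counted over visits. Table 7 puts the two weight criteria on separate lines, and the table specifications may well give each its own row. This stands: a reader might infer that the sponsor will publish a merged weight figure, and the documents do not support that. They support only that the rule, as worded, leads there.

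The reply does not remove the gap. If the tables have two rows, a subject who meets both criteria at different times belongs in both, while 14.3 counts that subject once and does not say where. If they have one row, the protocol is not followed. SAP 14.2 also states its splits when it wants them, for example by gender for hemoglobin, hematocrit and uric acid.

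A reader might also infer that high and low values in general are merged in breach of the protocol. That is not supported:

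- The protocol requires separation for body weight only. Protocol 9.7.3 plans laboratory PCI counts with no rule on direction ("The number and percentage of subjects with potentially clinically important post-baseline laboratory values will be summarized by treatment group and timepoint"), and 9.7.4 plans no such count for blood pressure or pulse.
- For laboratory values, SAP 14.2 already shows direction in low/normal/high shift tables and in summaries of the post-Baseline minimum and maximum.
- Table 8 has high criteria only. Its entry "QTcB or QTcF: change from Baseline" leaves open whether the two corrections share a row, but the QTcF categories in SAP 14.4 give the rates above 500 msec and for change above 60 msec on their own.

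Finally, the study is descriptive, with no hypothesis testing, and direction can be recovered from the listing. This limits the harm, but it does not supply the counts that 9.7.4 promises.

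**Conclusion.** The point holds for body weight. Protocol 9.7.4 requires separate counts of gains and losses of 7% or more. SAP 14.3 does not repeat this, its numerator and once-only rule taken literally pool the two, and SAP 19 records no departure. No other planned output replaces the missing counts and percentages.

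The conclusion rests on the literal wording and on the table specifications being unavailable. If they split the rows, the output would largely meet the protocol and the remaining defect would be one of wording. The size cannot be derived from the documents. The range of 12.6% to 25.2% rests on an assumed loss count, an assumed gain rate, full enrolment and no overlap. It shows what a pooled row could conceal and predicts nothing about this study. The same silence on direction for blood pressure, pulse and laboratory values, and the shared QTc entry, are matters of clarity and not conflicts with the protocol.

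**What to change.** In SAP 14.3, state that for weight the numerator and the once-only rule apply per criterion, that is, per direction. Report subjects with an increase of 7% or more and subjects with a decrease of 7% or more as separate rows, by visit and overall post-Baseline. A subject who meets both over the study then appears once in each row. Check that the table specifications agree.

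Optional, for clarity only: use the same per-direction wording for blood pressure, pulse and the two-sided laboratory criteria, and say whether QTcB and QTcF have separate rows in Table 8.

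The cost is one clause and one extra table row for weight. No new data are needed, and the threshold does not change.
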